All study-related documentation at Australian sites will be maintained for 15 years following completion of the study, or until 2 years following the date that the last marketing application for the study drug is approved, or if no marketing application is filed, or such application is not approved, for 2 years after the formal discontinuation of clinical development of the study drug – whichever is later.

Signed consent forms from Australian participants will not be collected by the Sponsor or their representative. They must be filed, as appropriate, at each site.

Section 11.10 Clinical Study Report

A Clinical Study Report which summarises and interprets all the pertinent study data collected for the MoST CRESTONE population (population of patients enrolled in Australia) will be issued, which may form the basis of a manuscript intended for publication.

HER2	Human Epidermal Growth Factor Receptor 2	
HER3	Human Epidermal Growth Factor Receptor 3	
IV	Intravenous	
MoST	Molecular Screening and Therapeutics Study	
NCI	National Cancer Institute	
NE	Not Evaluable	
NON-CR	Non Complete Response	
NON-PD	Non Progressive Disease	
NRG1	Neuregulin-1	
NSCLC	Non-Small Cell Lung Cancer	
ORR	Objective Response Rate	
OS	Overall Survival	
PCM1	Pericentriolar Material 1	
PD	Progressive Disease	
PFS	Progression-free Survival	
РК	Pharmacokinetic	
PMEPA1	Prostate Transmembrane Protein, Androgen Induced 1	
PR	Partial Response	
PT	Preferred Term	
QTcF	QT Interval Corrected According to Fredericia's Method	
RECIST	Response Evaluation Criteria in Solid Tumors	
SAE	Serious Adverse Event	
SAP	Statistical Analysis Plan	
SD	Stable Disease	

ABBREVIATION	DEFINITION	
SOC	System Organ Class	
STMN2	Stathmin 2	
TEAE	Treatment-Emergent Adverse Event	
TESAE	Treatment-Emergent Serious Adverse Event	
WHO	World Health Organization	

1. INTRODUCTION

This Statistical Analysis Plan (SAP) describes the statistical methodology and analyses to be conducted for Elevation Oncology, Inc. protocol ELVCAP-001-01 (Version 7.0). Any deviations from this analysis plan will be substantiated by sound statistical rationale and will be documented in the final clinical study report. The clinical study report will include all planned analyses defined in this SAP and any deviations from the planned analyses.

2. STUDY OBJECTIVES

Primary Objective: the primary objective of this study is to determine the objective response rate (ORR) by independent radiologic review to single agent seribantumab (anti-HER3 monoclonal antibody therapy; 3,000 mg IV weekly) in patients with centrally confirmed Neuregulin-1 (NRG1) gene fusion positive advanced cancer according to Response Evaluation Criteria in Solid Tumors (RECIST) v1.1.

Secondary Objectives: the secondary objectives of this study include the following:

- To determine the overall efficacy of single agent seribantumab in NRG1 gene fusion positive patients with various solid tumors through the assessment of the following clinical outcome parameters:
- Duration of Response (DoR) by independent radiologic review
- ORR and DoR by investigator assessment
- Progression-free Survival (PFS) by independent radiologic review and investigator assessment
- Overall Survival (OS)
- Clinical Benefit Rate (CBR) [Complete Response (CR), Partial Response (PR), Stable Disease (SD) ≥24 weeks] by independent radiologic review and investigator assessment
- To describe the safety profile of seribantumab

Exploratory Objectives: the exploratory objectives for this study are:

- To evaluate the pharmacokinetics (PK) of the seribantumab dosing schedule in patients with NRG1 gene fusion positive advanced solid tumors
- To evaluate if mechanistically linked exploratory biomarkers from tumor tissue or blood samples correlate with clinical outcomes
- To evaluate changes from baseline in quality of life, as measured by the European Organization for Research and Treatment of Cancer (EORTC) Quality of Life Questionnaire-Core 30 (QLQ-C30)

3. STUDY OVERVIEW

3.1. Study Design

This study is an open-label, international, multi-center, Phase 2 study in adult patients with advanced or metastatic solid tumors, which harbor the NRG1 gene fusion based upon local testing. The design of the study is summarized in Figure 1.

All patients will be determined to be NRG1 gene fusion positive based on local testing of tumor tissue per local laboratory directed analyses prior to initiating further screening procedures. After all screening procedures and determination of eligibility for study treatment have been completed, eligible patients will be assigned by the Sponsor to the appropriate cohort based upon prior treatment history. Patients will be assigned to Treatment Cohorts as follows:

Cohort 1: Patients with NRG1 gene fusions who are ERBB/HER2/HER3 treatment-naïve AND harbor NRG1 gene fusions with an EGF-like domain intact. Cohort 1 will include at least 55 patients with tumors that progressed on or are intolerant to ≥ 1 prior standard first-line therapy in the metastatic setting.

Cohort 2: Enrollment to Cohort 2 was closed under Protocol Version 5.0/Protocol Administrative Letter 8.0. Patients with NRG1 gene fusions with an EGF-like domain intact, who received ≥ 1 prior standard first-line therapy in the locally advanced or metastatic setting including at least one ERBB/HER2/HER3 directed treatment are ineligible for study participation.

Cohort 3: Enrollment to Cohort 3 was closed under Protocol Version 5.0 and later. Patients with NRG1 fusions without an EGF-like domain (including but not limited to NRG1-PMEPA1, NRG1-STMN2, PCM1-NRG1 and INTS9-NRG1) and patients with NRG1 fusions and other molecular aberrations lacking standard treatment options, AND patients unable to provide tissue for central confirmation of NRG1 gene fusion status are ineligible for study participation under Protocol Version 5.0.

*Cohort 1 will include at least 55 patients that have received ≥1 prior standard first-line therapy in the metastatic setting. **More than 10 patients may enroll under Cohorts 2 and 3 with Sponsor approval. Shaded box indicates cohort is closed to enrollment

EGF = epidermal growth factor; ERBB = receptor tyrosine-protein kinase erbB-3; HER = human epidermal growth factor receptor; NRG1 = Neuregulin-1

3.2. Seribantumab Dosing

Starting with Protocol Version 4.0 and later, eligible patients will receive seribantumab 3,000 mg 1-h IV once weekly until patients meet one or more protocol specific study treatment discontinuation criteria.

Prior to Protocol Version 4.0, treatment for all eligible patients consisted of an initial Induction (Induction Regimen 1: 3,000 mg x 1 week followed by 2, 000 mg once weekly dosing x 3 weeks; Induction Regimen 2: 3,000 mg once weekly dosing x 4 weeks) followed by Q2W maintenance dosing with 3,000 mg seribantumab.

3.3. Randomization and Blinding

This is an open-label non-randomized study.

3.4. Sample Size Determination

The trial is designed to provide statistically persuasive evidence of a clinically meaningful effect of seribantumab if the lower boundary of a 2-sided 95% exact binomial confidence interval (CI) about the estimated ORR exceeds a minimal threshold of 20%. This threshold for level of evidence for benefit would be consistent with the standard used for approved targeted therapies for genomically defined populations of patients who stop responding to previous standard therapies. A sample size of 55 patients with central confirmation of NRG1 gene fusion status, who have been enrolled and treated with either the 12-Week Target Induction Regimen and transitioned without interruption to weekly dosing (Clinical Protocol Version 3.0), or once weekly dosing from the time of enrollment (Clinical Protocol

Version 4.0 or later) is planned in the cohort 1 primary efficacy analysis population. Patients in the safety run-in (enrolled under Clinical Protocol Version 2.0 or earlier) will be included if they received seribantumab at 3,000 mg QW beyond induction/re-induction. This sample size will provide approximately 90% power for the lower bound of the 95% CI to exclude the pre-specified threshold of 20% for positivity assuming the ORR is 40% with seribantumab treatment.

3.5. Duration of Study

The expected duration of the study is 3 years.

3.6. Disease Assessments

For all consented patients assigned to one of the treatment cohorts after eligibility confirmation, treatment must start within 7 days following cohort assignment. Patients are expected to be treated until investigator-assessed progressive disease or unacceptable toxicity. Tumor assessments will be measured and recorded by the local radiologist beginning at weeks 6, 12, 18 and 24 (+/- 2 weeks) and subsequently every 8 weeks (+/- 2 weeks) through Week 48, followed by every 12 weeks (+/- 2 weeks) thereafter until disease progression and evaluated using the RECIST guidelines (version 1.1). All patients that discontinue treatment for reasons other than disease progression will have a scan performed at the time of the End of Treatment (EOT) visit.

In addition, an independent central review of scans may be conducted for patients assigned to cohort 1. All images may be submitted to a central imaging facility and may be assessed by independent reviewers in accordance with the Imaging Charter. After patients discontinue seribantumab treatment, survival information and information about subsequent therapies will be collected until death or study closure, whichever occurs first.

4. ANALYSIS POPULATIONS

This section defines the analysis populations to be used for the planned statistical analyses.

4.1. Efficacy Analysis Populations

Cohort 1 primary efficacy analysis population

The population will be used for the primary analysis of efficacy for registration purpose. It will include cohort 1 subjects enrolled in this study who meet all criteria listed below:

- Centrally confirmed NRG1 gene fusion
- Received at least one dose of seribantumab with the 3,000 mg IV QW dosing regimen (starting with Protocol Version 3.0 and later). Patients in the safety-run in (enrolled under Protocol Version 2.0 or earlier) will be included if they received seribantumab at 3,000 mg QW beyond induction/re-induction.
- Received at least one prior standard therapy in the locally advanced or metastatic setting
- At least one measurable lesion at baseline as assessed per RECIST Version 1.1

4.2. Safety Population

The Safety Population includes patients receiving at least one dose of seribantumab therapy across any of the three treatment cohorts (e.g., cohort 1, 2 and 3) and across any of the seribantumab dosing regimens. The safety population will be used for the overall safety analysis.

4.3. Pharmacokinetic Evaluable Population

The PK Evaluable Population includes all eligible patients who have at least one dose of seribantumab therapy, and from whom results of plasma concentrations are obtained for at least one sampling point which is suitable for analysis. The PK Evaluable Population will be used for PK analysis.

5. CLINICAL OUTCOME VARIABLES

This section provides endpoint definitions. For endpoints based on tumor assessments, such as ORR, DoR, PFS, and CBR, the definitions are the same for each endpoint whether the independent radiographic review assessments or investigator assessments are used per RECIST v1.1.

5.1. Primary Efficacy Endpoint

5.1.1. Objective Response Rate (ORR)

ORR is defined as the proportion of patients whose overall response is a confirmed CR or PR per RECIST v1.1. To be assigned a status of confirmed PR or CR, changes in tumor measurements must be confirmed by repeated assessments at least 4 weeks (28 days) after the criteria for response are first met. Tumor assessments after the initiation of new anticancer therapy should not be used to derive the ORR.

Patients with no evaluable post-baseline disease assessments (i.e., NE) will be considered non-responders and included in the denominator in the calculation of the ORR.

ORR based on independent radiologic review assessments is the primary efficacy endpoint in this study.

5.2. Secondary Efficacy Endpoints

5.2.1. Duration of Response (DoR)

Duration of response is defined as the time from the start date of CR or PR (whichever response status is observed first and subsequently confirmed), to the date of first documented radiographical progression of disease using RECIST v1.1, or death from any cause, whichever comes first. DoR will be calculated for patients who are responders, i.e., those who achieve a confirmed CR or PR.

DoR in days will be calculated as:

• DoR (days) = Date of PD or death (whichever is earlier) or Date of censoring – first date of PR/CR + 1

DoR in months will be calculated as:

• DoR (months) = 12*DoR (days)/365.25

DOR will follow the same censoring rules as PFS primary analysis in Table 1 in section 5.2.2.

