10.5. Efficacy Analysis

10.5.1. Primary Efficacy Endpoint for Cohort 1

Objective response rate (ORR) is the primary efficacy endpoint and will be analyzed based on the Cohort 1 primary efficacy analysis population.

ORR is determined by RECIST v1.1 (confirmed CR+PR) and will be assessed by independent radiographic review. To be assigned a status of confirmed PR or CR, changes in tumor measurements must be confirmed by repeated assessments at least 4 weeks (28 days) after the criteria for response are first met. Tumor assessments after the initiation of new anticancer therapy should not be used to derive the ORR. The point estimate of the ORR along with the 2-sided 95% exact Clopper-Pearson CI will be presented.

ORR will also be assessed by subgroups defined by the predefined factors listed in Section [10.8](#).

10.5.2. Secondary Efficacy Endpoints for Cohort 1

Secondary efficacy endpoints will be analyzed based on the Cohort 1 primary efficacy analysis population.

Objective Response Rate (ORR): ORR based on the investigator assessments will be analyzed similarly as described for the primary efficacy analysis (Section [10.5](#)). This is considered a sensitivity analysis.

Duration of Response (DoR): Duration of response is based on independent radiographic review. For patients who achieve a confirmed CR or PR, DoR is defined as the number of months from the start date of CR or PR (whichever response status is observed first and subsequently confirmed), to the date of first documented radiographical progression of disease using RECIST v1.1, or death from any cause, whichever comes first. DoR will be calculated for patients who are responders, i.e., those who achieve a confirmed CR or PR. The initiation of new anticancer therapy will mean the end of the response for the calculation of DoR. Responders who have not experienced disease progression, death, or new anticancer therapy at the time of the analysis will be censored at the date of the last tumor assessment. If no tumor assessments are available after the date of the first occurrence of response, the patient will be censored on the date of the first occurrence of the response. DoR will be estimated using the Kaplan-Meier method. The median DoR and the proportion of responders with durable responses at 6 months or 12 months will be estimated along with 95% CI.

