DoR by investigators: DoR based on the investigator assessments will be analyzed similarly as described for the respective endpoint based on the independent radiographic reviews. This is considered a sensitivity analysis.

Progression-free Survival (PFS): PFS is defined as the time from the date of seribantumab treatment initiation (Dose 1) to the first documented radiographical progression of disease using RECIST v1.1, or death from any cause, whichever comes first. The Kaplan-Meier method will be used to estimate PFS. In addition to the Kaplan-Meier plot of PFS, the median PFS time, 6-month, and 12-month PFS rates will be estimated along with 95% CI. PFS analysis will be performed separately based on central radiographic review and investigator assessments. Additional sensitivity analysis of PFS may be performed using different censoring rules. These sensitivity analyses will be detailed in the SAP.

Overall Survival: OS is defined as the time from the date of treatment seribantumab treatment initiation (Dose 1) to the date of death from any cause. The Kaplan-Meier method will be used to estimate OS. In addition to the Kaplan-Meier plot of OS, the median OS time, 6-month, and 12-month survival rates will be estimated, along with 95% CI.

Clinical Benefit Rate (CBR): Clinical benefit rate is defined as the proportion of patients who achieve PR, CR, or SD which is maintained through at least 24 weeks per RECIST v1.1. Tumor assessments after the initiation of new anticancer therapy should not be used to derive the CBR. Patients with no baseline disease assessment or no evaluable post-baseline disease assessments (i.e., NE) or with ongoing SD but short of 24 weeks at the time of analysis will be considered as not having attained clinical benefit and included in the denominator in the calculation of the CBR. CBR will be summarized similarly as the ORR with both point estimate and 95% Clopper-Pearson CI provided. CBR analysis will be performed separately based on central radiographic review and investigator assessments.

Secondary efficacy endpoints will also be assessed by subgroups defined by the predefined factors listed in Section 10.8.

10.5.3. Exploratory Efficacy Analysis for Cohorts 2 and 3

Efficacy analyses of the primary efficacy endpoint and secondary efficacy endpoints for Cohorts 2 and 3 will be performed separately using the same methods described above. For the ORR, DoR, CBR, and PFS endpoints, investigator assessments will be used.

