5.2.2. Progression-free Survival (PFS)

Progression-free survival is defined as the time from the date of seribantumab treatment initiation (Dose 1) to the first documented radiographical progression of disease using RECIST v1.1, or death from any cause, whichever comes first.

PFS in days will be calculated as:

• PFS (days) = Date of PD or death (whichever is earlier) or Date of censoring – first dose date + 1

PFS in months will be calculated as:

• PFS (months) = 12*PFS (days)/365.25

The following table summarizes the PFS censoring rules:

Table 1:Progression Free Survival		Survival Censoring Rules	
		Primary analysis	Sens

	Primary analysis	Sensitivity analysis		
	(Censoring rules)	(Censoring rules)		
No PD, no death, no NACT initiated	Censored at last tumor assessment. If no evaluable tumor assessment, censored on the first dose date.	Censored at last tumor assessment. If no evaluable tumor assessment, censored on the first dose date.		
No PD, no death, NACT initiated	Censored at the last tumor assessment prior to NACT. If no evaluable tumor assessment, censored on the first dose date.	Censored at last tumor assessment regardless of NACT. If no evaluable tumor assessment, censored on the first dose date.		
PD or death, no NACT initiated	PFS event at the date of PD or death	PFS event at the date of PD or death		
PD or death prior to or on date NCAT initiated if patient received the NACT	PFS event at the date of PD or death	PFS event at the date of PD or death		
PD or death after NACT	Censored at the last tumor assessment prior to NACT	PFS event at the date of PD or death		
PD or death after 1 missed tumor assessment	PFS event at the date of PD or death	PFS event at the date of PD or death		
PD or death after 2 or more missed tumor assessment	Censored at last tumor assessment prior to PD or death	PFS event at the date of PD or death		
Abbreviations: PD = progressive disease; PFS = progression-free survival; NACT = new anticancer therapy				

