6.3. Efficacy Analyses

All efficacy analyses will be performed by cohort. Analyses for the cohort 1 primary efficacy analysis population will be intended to support a potential registration With the exception on the handling of tumor assessments after the initiation of new anticancer therapy as described in Sections 5.1 and 5.2, all data from scheduled or unscheduled assessments will be included in the efficacy analyses.

All efficacy analysis will be analyzed by investigator assessments only, independent radiographic review was not done due to Sponsor decision to end the study prior to full enrollment.

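### The SAP censors duration of response at new anticancer therapy and after missed scans, contrary to the protocol, without listing the change or planning an output under the protocol rule

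*SAP*

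**What the plan says.** Protocol 10.5.2 runs DoR from the first response that is later confirmed to radiographic progression (PD) or death. Two further sentences deal with new anticancer therapy (NACT). The first, repeated in the synopsis, is "The initiation of new anticancer therapy will mean the end of the response for the calculation of DoR". The second sets who is censored: "Responders who have not experienced disease progression, death, or new anticancer therapy at the time of the analysis will be censored", at the last tumor assessment, or at the date of first response if no later assessment exists. There is no missed-scan rule for DoR. Investigator-assessed DoR takes the same approach: "DoR based on the investigator assessments will be analyzed similarly as described for the respective endpoint based on the independent radiographic reviews".

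SAP 5.2.1 keeps the PD-or-death definition, omits the NACT sentence and adds: "DOR will follow the same censoring rules as PFS primary analysis in Table 1 in section 5.2.2". In the primary column of Table 1 (SAP 5.2.2), PD or death after NACT is "Censored at the last tumor assessment prior to NACT", and NACT without PD or death is handled the same way. PD or death after two or more missed assessments is "Censored at last tumor assessment prior to PD or death".

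SAP 6.3.4 plans a single Kaplan-Meier analysis of DoR. The alternative censoring column of Table 1 is called for only under PFS, in SAP 6.3.2. SAP 6.3 adds: "All efficacy analysis will be analyzed by investigator assessments only, independent radiographic review was not done due to Sponsor decision to end the study". Section 8 lists the missing central review, two dropped exploratory endpoints, one phrase removed from a population criterion, and the dropped Cohort 2 and 3 efficacy analyses. It does not mention DoR censoring.

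**The concern.** The same responder can count as an event under the protocol and as censored under the SAP. The two rules estimate different things: time to PD, death or new therapy, against time to PD or death with follow-up cut at new therapy. Either can be defended. The difficulty is that the rule changed, the SAP's own list of changes does not say so, and nothing planned lets a reader see DoR as the protocol defined it.

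At stake are all the outputs in SAP 6.3.4: event and censoring counts, the median and quartiles, minimum and maximum, the 6- and 12-month rates and the plot. The mismatch reaches the only DoR now produced, the investigator-assessed one, because SAP Section 5 gives one definition for both kinds of reader. The trial is open-label, and this first SAP version (11 March 2024) already records the decision to end the study. Nothing suggests that data drove the choice, but the timing makes disclosure more important.

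**Working it through.** **Design figure.** The documents state no DoR figure. Their one design figure, about 90% power for ORR, reproduces at 89.3% (at least 18 of 55 responses needed; lower exact limit 20.7%) and does not depend on DoR censoring.

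**One patient under three rules.** Assume response at Week 6, last scan Week 24, NACT at Week 28, death at Week 44. The SAP formulas are days = end - start + 1 and months = 12 × days / 365.25.

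- Protocol rule, response ends at NACT: (28 - 6) × 7 + 1 = 155 days, an event at 5.1 months.
- SAP rule, censored at the last scan before NACT: (24 - 6) × 7 + 1 = 127 days, censored at 4.2 months.
- Table 1 sensitivity column, which ignores NACT: (44 - 6) × 7 + 1 = 267 days, an event at 8.8 months. For patients with NACT but no PD or death that column reads "Censored at last tumor assessment regardless of NACT".

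Neither column of Table 1 gives the protocol result, so extending the PFS sensitivity analysis to DoR would not supply it.

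**Effect on the median.** Let f be the share of response ends that are NACT, with constant hazards and non-informative censoring. If the protocol-rule hazard is λ, the SAP rule leaves (1 - f)λ, so the median ratio (SAP/protocol) is 1/(1 - f):

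| f | 0 | 5% | 10% | 20% | 30% |
|---|---|---|---|---|---|
| ratio | 1.00 | 1.05 | 1.11 | 1.25 | 1.43 |

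**Effect of one responder on the rates.** The assumed layouts have N responders, N/2 PD events evenly spaced from month 3 to month 15, one affected responder, and the rest censored at month 18. N = 8 is 40% of the 20 interim patients. N = 22 is 40% of the planned 55, which was not reached, so it is an upper illustration. N = 12 lies between.

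*NACT case:* NACT at month 5 (event under the protocol), last scan at month 4.6 (censored under the SAP).

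| N | 6-month, protocol | 6-month, SAP | 12-month, protocol | 12-month, SAP |
|---|---|---|---|---|
| 8 | 6/8 = 75.0% | 7/8 = 87.5% | 4/8 = 50.0% | 7/8 × 4/6 = 58.3% |
| 12 | 9/12 = 75.0% | 11/12 × 9/10 = 82.5% | 7/12 = 58.3% | 11/12 × 7/10 = 64.2% |
| 22 | 18/22 = 81.8% | 20/22 × 18/19 = 86.1% | 13/22 = 59.1% | 20/22 × 13/19 = 62.2% |

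*Missed-scan case:* response Week 6, last scan Week 24, Weeks 32 and 40 missed, death Week 44. This is an event at 8.8 months under the protocol and censored at 4.2 months under the SAP.

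| N | 6-month, protocol | 6-month, SAP | 12-month, protocol | 12-month, SAP |
|---|---|---|---|---|
| 8 | 87.5% | 87.5% | 50.0% | 58.3% |
| 12 | 10/12 = 83.3% | 82.5% | 58.3% | 64.2% |
| 22 | 19/22 = 86.4% | 86.1% | 59.1% | 62.2% |

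At N = 22 the SAP values use the rounded 4.2 months. With the unrounded 4.17 they are 85.9% and 62.0%. In these layouts NACT censoring raises both rates. Missed-scan censoring raises the 12-month rate but leaves the 6-month rate unchanged or slightly lower.

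**The case against.** The strongest objection is that the protocol rule is partly inferred. Its DoR definition names only PD and death, the word event is not used, and no date is attached to the end of response at NACT. That is a fair account of the wording. But the censoring sentence excludes responders with NACT, and under the SAP reading that exclusion would have no purpose. If the sponsor thought the text ambiguous, the SAP should say how it was resolved.

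The missed-scan part is less clear-cut. The protocol leaves detailed methodology to the SAP, and the SAP adds the same rule for PFS, where the protocol is also silent. For DoR, however, the protocol does state who is censored, and a responder with PD or death is not in that group.

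The effect may also be nil. Treatment is expected to continue to PD, other antineoplastic therapy is barred while on treatment, and a scan is due at the end-of-treatment visit before any new therapy (Protocol 6.5 and Table 4, note 12). This limits NACT before PD without excluding it: Protocol 5.4 allows stopping because the investigator sees a need for other treatment, and Protocol 3.1 ends scanning once new therapy starts. Finally, the SAP states its rule openly and DoR is a secondary, descriptive endpoint. Both points limit the severity, but neither supplies the missing disclosure or output.

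**Conclusion.** The concern holds. SAP 5.2.1 contradicts Protocol 10.5.2 on new anticancer therapy and adds missed-scan censoring that the protocol's DoR rule does not allow. Section 8 is silent, and no planned output shows the protocol rule. This is a difference of estimand, not demonstrated bias.

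Its size is unknown because the documents give no responder count, NACT share or missed-scan frequency. The median ratio runs from 1.00 with no NACT to 1.43 at f = 30%. In the assumed layouts one NACT responder shifts the 6-month rate by 4.3 points (N = 22) to 12.5 points (N = 8). These figures rest on constant hazards or the stated layouts, and on reading NACT as ending DoR on its start date. ORR and its power are untouched. The point should be fixed because a named secondary endpoint has two incompatible rules and, with few responders, a single patient can move the result.

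**What to change.** Preferred: restore the protocol rule through three linked edits in SAP 5.2.1 and one addition in 6.3.4.

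1. Definition: DoR ends at the earliest of radiographic PD, death from any cause, or start of NACT.
2. Formula: use the earliest of those three dates, or the censoring date, minus the first response date, plus 1.
3. Censoring: responders with none of the three are censored at the last tumor assessment, or at the first response date if there is no later one. This replaces the reference to Table 1.
4. SAP 6.3.4: add a DoR sensitivity analysis using the Table 1 primary censoring rules.

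Alternative: keep Table 1 censoring as the main DoR analysis, list and justify it in Section 8, and add one Kaplan-Meier output under the protocol rule. In that case also replace Table 1's first-dose fallback by the first response date for DoR. First dose precedes the start of DoR, although a confirmed responder should never trigger that fallback.

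The cost is a few sentences and one extra Kaplan-Meier output. No new data are needed, since NACT is already collected at each survival follow-up (Protocol Table 4, note 15; SAP 6.2.9). The downside is two DoR results to explain, and the protocol-rule result may look less favourable.
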